## STATEMENT OF COMPLIANCE FOR NON DRUG OR DEVICE CLINICAL TRIALS

This document is a protocol for a clinical research study. The study will be conducted in compliance with all stipulations of this protocol, the conditions of ethics committee approval, the [NHMRC National Statement on Ethical Conduct in Human Research](#) (as updated) and the [Handbook for Good Clinical Research Practice \(GCP\)](#). [The Therapeutic Goods Act has adopted ICH Guideline for Good Clinical Practice.](#)

## 1. GENERAL INFORMATION

Study Protocol: CanaCareTrial, 29th July 2020.

Partly funded by Seed Funding Scheme: Mental Health, Drug and Alcohol Comorbidity.  
Study Sponsor: University of Sydney.

## 2. SYNOPSIS

CanaCare is an interdisciplinary clinic and translational research study focused on health and wellness promotion for individuals who have experienced mental and physical health challenges due to a variety of circumstances, and are seeking assistance with lifestyle advice and choices which may lead to improved wellbeing, social integration, and engagement in their communities. The CanaCare team consists of a physician, accredited practising dietitians, accredited exercise physiologists, registered physiotherapists, registered psychologists, social workers, and a pharmacist. The clinic will utilise a person-centred approach for the delivery of a holistic assessment of each individual's physical and psychological health status and goals. The clinic team and the client will together structure a plan for reaching these goals which may include structured exercise (Linke et al, 2015; Hallgren et al, 2017, Lynch et al, 2013), nutritional changes (Opie et al, 2015; Teasdale et al, 2017), medication review, psychological support and counselling, control of substance use, referral to other health care practitioners for ongoing care or specialised tests, as well as behavioural support and ongoing feedback. Participants will be those individuals who have engaged with the Cana Communities not-for-profit organisation in any of its ongoing programs in NSW. The organisation supports individuals who have a wide variety of mental health conditions, disabilities, substance-use disorders, have been recently released from incarceration, those who have experienced loneliness and social isolation or disengagement, homelessness, domestic violence, refugees and those who have experienced trauma in its many forms.

Our primary outcome will be Happiness measured using the Oxford Happiness Scale, measured at baseline and 6 months. Secondary outcomes will include depressive symptoms, anxiety, sleep, quality of life, physical activity levels, dietary intake, body composition, exercise capacity, and functional mobility, as well as social integration/stability in domains of work, education, residential status, and relationships. (If there is no specific

scale, we will just ask the question about these areas before and after, to determine job status, living situation, etc).

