##### **Primary Hypotheses**

Participation in the interdisciplinary CanaCare program, utilising a person-centred approach, will result in a significant improvement in the Oxford Happiness Score after 6 months.

Secondary aims of the study will be to assess the effect of the study on improvements in nutrition and health status, functional status, sleep quality, physical activity participation, neuropsychological outcomes (including depression, anxiety, self-esteem, and empathy), maximal aerobic capacity, muscle strength, physical performance, anthropometric parameters and body composition (including fat mass, fat free mass and bone mineral density).

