**6.2 POPULATION / SAMPLE SIZE INCLUDING POWER CALCULATION**

We will recruit men and women who have had any interaction with Cana Communities. This may be via provision of services, general inquiries or individuals who have been identified as suitable for the CanaCare Clinic study by Cana Communities staff and volunteers.

Our sample size calculation is based on a pilot randomised controlled trial in a non-clinical adult population, who were randomly allocated to one of two positive psychology interventions. Effect size and sample size estimates based on the changes in the Oxford Happiness Questionnaire following each intervention are summarised below.

Intervention	Pre (mean)	Post (mean)	Mean difference	Baseline SD	Hedges g	Sample Size
Happiness	3.81	4.14	0.33	0.84	0.38	57
Gratitude	3.83	4.34	0.51	0.67	0.75	16

Sample size estimates were based on within-group changes in the Oxford Happiness Questionnaire, with a critical alpha of 0.05, and a power of 0.8, using a two-tailed t-test. Based on the data above, we would require 57 participants to detect a significant change in the Oxford Happiness Questionnaire. As we are recruiting a marginalised population, it is possible that the effect size following the intervention will be larger, and therefore we believe this reflects a conservative sample size estimate.

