Each participant will be linked with a Cana Communities volunteer from the community who will be his/her primary coordinator of care, depending on the most important or urgent goal or wellness need identified. This person will be responsible for follow-up by telephone on a weekly basis initially, to assist with the adoption of the Wellness program elements.

Follow-up will be planned for 3 months and 6 months to re-evaluate and re-set goals (either in-person or online). The participant will be accompanied/supported by their Cana support person if needed.

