## 6.4 STATISTICAL ANALYSES

Descriptive data on participant characteristics and all outcomes will be generated using parametric and non-parametric summary statistics as appropriate to the distribution of the data. Relationships between variables of interest will be analysed via simple and multiple regression models or Spearman's correlation analyses as appropriate. Outcomes over time will be analysed through ANCOVA repeated measures with main effect of time and additional covariates as identified by review of the baseline data. Effect sizes will be generated for major primary and secondary outcomes of interest. Adherence to programmatic elements will be calculated and all adverse events, related and unrelated to study protocols will be tabulated. A p value of less than 0.05 will be accepted as a threshold of statistical significance. Clinical relevance of any changes observed in health status or behaviours will be determined by comparison to existing data on clinically meaningful changes in the relevant outcomes.

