## 9. OUTCOMES

Table 1 illustrates the CanaCare Clinic primary and secondary outcomes. All participants will complete the Oxford Happiness Questionnaire. Other outcome measures will be completed if they are relevant to the participant's goals.

Table 1. CanaCare Primary and Secondary Outcomes.

Primary Outcomes
1. Oxford Happiness Questionnaire score
Secondary Outcomes
1. Neuropsychological Outcomes 
 
1.1. Self-efficacy 
 
1.1.1. Ewart's Self Efficacy Scale
 
 
 
1.2. Empathy 
 
1.2.1. Toronto Empathy Scale
 
 
 
1.3. Quality of Life 
 
1.3.1. Short Form 36 Health Survey Questionnaire (SF-36)
 
 
 
1.4. Depression 
 
1.4.1. Patient Health Questionnaire-9 (PHQ-9)
 
1.4.2. Hamilton Depression Rating Scale (HAM-D)
 
 
 
1.5. Anxiety 
 
1.5.1. Generalised Anxiety Disorder 7-Item (GAD-7)
 
 
 
1.6. Post-traumatic Stress Disorder Symptoms 
 
1.6.1. Post-traumatic Stress Disorder Symptom Scale – Interview for DSM-5 (PSS-I-5)
 
 
 
1.7. Mindfulness 
 
1.7.1. Mindfulness Attention Awareness Scale
 
 
 
1.8. Experiential Avoidance 
 
1.8.1. Acceptance and Action Questionnaire (AAQ)
 
 
 

2. Aerobic Capacity 
 
2.1. Maximal aerobic capacity (VO2peak) 
 
2.1.1. Graded treadmill test to voluntary fatigue with indirect calorimetry
 
 
 

3. Muscular Strength 
 
3.1. One Repetition Maximum (1RM) (seated leg press, unilateral knee extension, chest press, and seated row)
 

4. Nutrition 
 
4.1. Short Form Food Frequency Questionnaire (SFFFQ)
 
4.2. CanaCare Dietary Questionnaire
 

5. Physical Performance 
 
5.1. 6-minute Walk Test (6MWT)
 
5.2. Short Physical Performance Battery
 
5.3. Balance (static and dynamic)
 

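### The happiness score is not scheduled at the existing 3-month review, so the named analysis in its usual form rests on participants with a 6-month score and non-random loss would bias the change, in a direction that depends on who leaves

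*Protocol*

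**What the plan says.** - **Timing of the primary outcome.** The Synopsis (section 2): "Our primary outcome will be Happiness measured using the Oxford Happiness Scale, measured at baseline and 6 months". The primary hypothesis in section 4 is set at the same point: the programme "will result in a significant improvement in the Oxford Happiness Score after 6 months".
- **Contacts.** Section 6.3: "Follow-up will be planned for 3 months and 6 months to re-evaluate and re-set goals (either in-person or online". The 3-month contact is given a care purpose and no outcome measure.
- **Who is measured.** Section 9: "All participants will complete the Oxford Happiness Questionnaire". It gives no time points.
- **Analysis.** Section 6.4: "Outcomes over time will be analysed through ANCOVA repeated measures with main effect of time", with covariates to be chosen after review of the baseline data.
- **Sample size.** Section 6.2 plans on a within-group change "with a critical alpha of 0.05, and a power of 0.8, using a two-tailed t-test" and arrives at 57.

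Only one group is described. Section 6.5 lets participants withdraw at any time. No attrition rate is given anywhere.

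**The concern.** With two time points, a participant who has no 6-month score has no post-baseline happiness data at all. Repeated-measures ANCOVA as usually run needs complete rows, so that person leaves the primary analysis and the estimate describes completers.

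The Synopsis describes people with substance-use disorders, homelessness or recent release from incarceration. Loss related to how people are faring is plausible there, though the protocol does not say so. With no comparison group, nothing in the design would reveal or offset such selection: whatever it does to the completers' mean change goes straight into the primary result.

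The schedule is what makes this a protocol matter. A later analysis plan can choose another model or missing-data method, but it cannot recover a 3-month score that was never collected.

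**Working it through.** **1. The plan's own figure.** Section 6.2, planning row: "Happiness 3.81 4.14 0.33 0.84 0.38 57". For a paired t-test, power comes from the noncentral t distribution with n − 1 degrees of freedom and noncentrality 0.38 × √n. At n = 57, two-sided alpha 0.05, power is 0.805, so 57 reproduces (as does 16 for g = 0.75). It is therefore the number needed *with both scores*. If 20% or 30% of 57 had no 6-month score (assumed rates), 45 or 39 would remain and power would be 0.70 or 0.64.

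**2. Inputs for the bias.** From the protocol: SD 0.84 (section 6.2) and the visit times. Assumed, because the protocol gives no values: true change zero; correlation 0.7 between adjacent visits and 0.6 between baseline and 6 months; 30% loss; logistic loss with a log-odds slope of 1 per SD of the driving variable.

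**3. Formula.** Let c3 and c6 be the changes from baseline to 3 and 6 months, and s the standardised variable that drives loss. With normal scores,

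bias in completers = Cov(c6, s) × E(s | stay).

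If p is the probability of staying (mean 0.70), E(s | stay) = E[p(1 − p)] / 0.70 ≈ 0.175 / 0.70 = 0.25.

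- *Loss follows 3-month decline.* Cov(c6, c3) = 0.84² × (1 − 0.7 − 0.6 + 0.7) = 0.282. SD(c3) = 0.84 × √(2 × 0.3) = 0.651. Bias = (0.282 / 0.651) × 0.25 = 0.434 × 0.25 = **+0.11**.
- *Loss follows 6-month decline.* SD(c6) = 0.84 × √(2 × 0.4) = 0.751. Bias = 0.751 × 0.25 = **+0.19**.
- *Loss follows low baseline.* Cov(c6, s) = −0.84 × (1 − 0.6) = −0.336. Bias = −0.336 × 0.25 = **−0.084**; simulation runs gave −0.08 to −0.09.
- *Random loss.* **0**.

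**4. Simulated trials of 57, loss following 3-month decline, no true change.**

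| Loss | Completers' mean change | Significant at 5% |
|---|---|---|
| 10% | +0.04 | 7% |
| 20% | +0.07 | 10% |
| 30% | +0.11 | 16% |
| 40% | +0.15 | 21% |

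**5. What a 3-month score would do (30% loss, no true change).** The estimate is now a likelihood-based one that keeps everyone with a baseline score.

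| Loss mechanism | Completers | With 3-month score |
|---|---|---|
| 3-month decline, all seen at 3 months | +0.11 | 0.00 |
| 3-month decline, half of those lost leave before 3 months | +0.11 | +0.03 |
| 3-month decline, all of those lost leave before 3 months | +0.11 | +0.08 |
| 6-month decline | +0.19 | +0.12 |
| Low baseline | −0.08 to −0.09 | 0.00 |

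In the third row the 3-month score adds nothing: a two-visit likelihood model gives the same +0.08. In the last row the likelihood model alone corrects the bias, with or without a 3-month score.

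**6. Same pattern with a real effect.** With a true change of 0.33 and correlation 0.5 between all visits, completers show 0.40 at 20% loss and 0.43 at 30% when loss follows 3-month change; the 3-month model returns 0.33. When loss follows 6-month change, completers show 0.48 and 0.54, and the 3-month model 0.43 and 0.48. When loss follows low baseline, completers show 0.26 and 0.22.

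**The case against.** The two-visit design is coherent. The hypothesis concerns change at 6 months, and with two visits the main effect of time is exactly that contrast. The 3-month contact has a stated care purpose, and leaving a questionnaire out of it contradicts nothing. **This stands:** the point is an improvement to the design, not an internal error.

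Section 6.4 does not say that participants without a 6-month score are excluded. It fixes no analysis set, missing-data rule or estimation method, and these are commonly left to an analysis plan. **This stands too:** exclusion is the conventional reading of the named method, not a stated rule, and the absence of a missing-data method is not the complaint. It does not reach the schedule.

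A reader might infer that the trial will overstate the benefit. The documents do not support that. They give no attrition rate and no information on who leaves, and loss driven by low baseline scores would understate the change.

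A reader might equally infer that a 3-month score would bring the bias to zero. That holds only if loss is explained by observed scores and those lost attend the 3-month review first. In this population some may well leave earlier.

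A control arm would not be a guaranteed remedy either: it would cancel the selection only if loss acted alike in both arms.

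**Conclusion.** The point holds in conditional form. The protocol places the primary outcome at baseline and 6 months only, leaves the existing 3-month review without it, and names a method that conventionally uses only participants with both scores. Non-random loss would then bias the before-after change. Under the stated assumptions at 30% loss, the bias runs from about −0.08 or −0.09 to +0.19 points, against a planned change of 0.33: roughly a quarter of it downwards (0.084 / 0.33 = 25%) to over half upwards (0.19 / 0.33 = 58%). Random loss gives none.

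Only the SD and the planned change come from the protocol. The loss rate, the correlations, and the mechanism and strength of loss are assumptions, so these figures illustrate scale and do not predict this trial's bias.

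**What to change.** 1. In the Synopsis and section 9, add the Oxford Happiness Questionnaire at the 3-month review already scheduled in section 6.3.
2. In section 6.4, analyse all participants with a baseline score in a likelihood-based mixed model with time as three categories. Adding the score while keeping a complete-rows analysis would not help.
3. Name the baseline-to-6-month contrast as the single primary test. With three visits the main effect of time would become an overall test across visits, so the contrast must be named to keep matching the hypothesis in section 4. This is a consequence of the change, not a fault in the present two-visit plan.
4. Add a sensitivity analysis for missing 6-month scores, for example with missing change set to zero, because the model cannot remove bias from loss that depends on the unseen 6-month score.

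**Cost:** one extra questionnaire at an existing contact and edits to the analysis section. There is some participant burden; section 8.2 itself lists fatigue and distress as questionnaire risks.

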### 3. RATIONALE / BACKGROUND

*“But equal treatment in an unequal society could still foster inequality”.*

Mathew Desmond (2016)

*“[Patient centred care] Medicine of the person, for the person, by the person, and with the person”.*

International College of Person-Centered Medicine (2019)

Cana Communities is a registered not-for-profit charity that was first established in 1975. The focus of the organisation is in helping people who are most in need, those who may have a mental health condition, substance-use disorders, are experiencing homelessness, are suffering from loneliness, and other factors which alienate them from society (Cana Communities, 2017). The organisation offers society’s most marginalised people support as they slowly reintegrate, and-transition into stable living. This is achieved through social support provided by staff and volunteers, supported housing, employment, and educational opportunities.

Across Australia there are numerous outreach programs provided by Cana Communities. To name a few, the De Porres House in Darlinghurst, established in 1975, provides transitional and permanent accommodation for men and women. Referrals can be made for individuals who have been released from correctional facilities, are homeless, and asylum seekers without financial government support. The Nagle House in Redfern is a residential home, established in 2012 with 10 single rooms; that provides a safe, transitional home for women who have experienced trauma. Since 2012, Cana Farm, situated on the outskirts of Sydney, has been offering much more than organic vegetables to their community. The farm employs 14 people in transitional employment, providing more flexibility than a regular workplace, which is vital for this cohort to succeed. The prison release support program at Cana Farm offers men at the *Compulsory Drug Treatment Correctional Centre* employment within the community, to assist in effective re-integration within society (Taguchi, 2017). The individuals that Cana Communities seeks to support are those who have experienced serious mental

and physical challenges in their life. Thus, by developing better life skills, their overall health and mental health have improved. There is a need to provide further support avenues for these individuals to improve their overall health and wellbeing. Health is defined as inclusive of physical, mental, and social well-being, and not purely the absence of disease (WHO, 2014). Aptly titled, *“All is not equal”*, the Australian Institute of Health and Welfare (AIHW) highlight the important role of social determinates of health in Australia (2018). There are significant disparities in the health outcomes of people living in poorer socioeconomic conditions. Disadvantaged Australians experience greater levels of disease risk factors and lower use of preventative health services, compared to those with a socioeconomic advantage (Australian Bureau of Statistics [ABS], 2010). There are other factors that can contribute to disadvantage that extend beyond financial factors, such as poor health, disability, low education, social support, limited community participation, low health literacy, and social exclusion, among others (AIHW, 2017). Statistically, 11.5 percent of Australians over the age of 15 years, experienced deep and persistent disadvantage due to unemployment, 11.2 percent with a long-term health condition or disability, and 15.3 percent of individuals dependent on income support. It has been shown that 62.1% of people aged 15-64 years with a mental or behavioural condition were employed, compared to 79.5% without a mental or behavioural condition (ABS, 2010). The World Health Organization (WHO) stipulates that social inequalities and disadvantage are the primary reason for unfair and avoidable differences in health status and longevity across groups within society (2008).

The aim of CanaCare is to offer support for individuals who have experienced disadvantage, and have sought engagement with the Cana Communities organisation. The Clinic will be available to all those who are seeking assistance with lifestyle advice and life choices which may lead to improved wellbeing, social integration, and engagement in their communities. The interdisciplinary clinic includes a physician, accredited practising dieticians, accredited exercise physiologists, registered psychologists, registered physiotherapists, social workers, and a pharmacist. All services and discussions will be conducted to align with the principles of person-centred care; to provide choice, responsibility and autonomy in important health matters that pertain to the individual. Mental health is defined as a state of well-being in which all people realise their potential, cope with daily stressors of life, work productively and fruitfully, and with the ability to contribute to their community (WHO, 2014). It is the aim of the CanaCare clinic to strive to achieve this definition of mental health for participants. The primary outcome in this study is Happiness (Ryan et al, 2001). This focus on happiness is intentionally broader than the lack of depression or negative affect, which traditionally have been the targets of mental health programs. Here, we take a much broader view of the goals of the clinic which are to assist with the integration of identified needs in the areas of mental, physical, emotional, and social aspects of wellbeing. Collectively, we anticipate that these factors will contribute to an improved sense of optimism, positive affect, life satisfaction, and purpose in life, all components of this construct of Happiness.

#### **4. AIMS / OBJECTIVES / HYPOTHESES**

The primary aim of the CanaCare program is to utilise a person-centred approach to care planning and delivery, provided in collaboration with an interdisciplinary team with the overall aim of improving the health and wellness for all participants.

##### **Primary Hypotheses**

Participation in the interdisciplinary CanaCare program, utilising a person-centred approach, will result in a significant improvement in the Oxford Happiness Score after 6 months.

Secondary aims of the study will be to assess the effect of the study on improvements in nutrition and health status, functional status, sleep quality, physical activity participation, neuropsychological outcomes (including depression, anxiety, self-esteem, and empathy), maximal aerobic capacity, muscle strength, physical performance, anthropometric parameters and body composition (including fat mass, fat free mass and bone mineral density).

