**6. RESEARCH PLAN / STUDY DESIGN**

**6.1. TYPE OF STUDY**

6-month translational study.

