### **6.3 STUDY DESIGN**

Participants will be accompanied by a support person from the Cana Communities volunteer pool to the University of Sydney study site or will be supported by their support person to access one of the three online platforms (mentioned above) at a designated time. The participants will initially meet/talk to [name] [name] [study physician] to identify their primary goals/reasons for wanting to take part in the research program. Depending on what the participants identify as their primary (life) goal or aspiration/s, the physical and medical history assessment will focus on areas relevant to their goals.

Participants will then meet with one or more allied health practitioners for additional assessments to be completed. The interdisciplinary team will consist of accredited dietitians, accredited exercise physiologists, social workers, registered psychologists, registered physiotherapists and pharmacists. These assessments may include questionnaires, structured interviews, counselling sessions, body composition testing, nutritional assessments, fitness assessments and drug reviews.

A case conference will be held with all health practitioners involved in the participants' care. Subsequently, a case conference will be held with the team and the participants, with their support person present, to discuss their assessments, and how they relate to their goals. Through discussions with the participant, initial components of the Wellness program will be made. This may include exercise, dietary changes, mental health strategies such as mindfulness or meditation or cognitive behavioural therapy, or lessening of substance use, as appropriate. The care provided by CanaCare will be in addition to the usual supports provided by Cana Communities for effective reintegration into work, housing support, and social relationship building, among other offerings.

The Wellness program may take place across different sites including the University of Sydney Camperdown campus, Cana Communities sites around Sydney and Cana Farm in Orchard Hills and via the secure online platform chosen. Programs may be supervised or unsupervised, as appropriate, and will be interdisciplinary in nature. Where relevant, the study physician may make referrals to the participant's general practitioner, a psychiatrist or specialist.

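### The primary hypothesis and secondary aims credit any improvement to CanaCare, but a one-group before-after study alongside other Cana supports can show only that scores changed

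*Protocol*

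**What the plan says.** Section 4 (Primary Hypotheses) puts the claim in one sentence: "Participation in the interdisciplinary CanaCare program, utilising a person-centred approach, will result in a significant improvement in the Oxford Happiness Score after 6 months". The aims listed after it are to "assess the effect of the study on improvements in nutrition and health status" and on a list of further outcomes.

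The design sections describe one group followed over time:

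- Section 6.1 gives the type of study only as a "6-month translational study".
- The Synopsis (Section 2) has happiness "measured using the Oxford Happiness Scale, measured at baseline and 6 months".
- Section 6.2: "Sample size estimates were based on within-group changes in the Oxford Happiness Questionnaire". The calculation uses a two-sided t-test at the 5% level with 80% power, and the requirement is 57 participants in total.
- Section 6.4 plans a repeated-measures ANCOVA with time as the main effect and covariates chosen after review of the baseline data. There is no group term.
- Section 6.3: "The care provided by CanaCare will be in addition to the usual supports provided by Cana Communities". The supports named there concern work, housing and social relationships.

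The protocol describes no control arm, waiting-list group or external comparison, and places no limit on causal interpretation.

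**The concern.** A hypothesis that says participation produces the improvement needs some estimate of what would have happened without participation. This plan has none. The change from baseline to 6 months is the sum of whatever CanaCare does and whatever else moves the score over the same half-year, and the planned test sees only the sum.

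The most concrete rival explanation is in the protocol itself. Participants have access to Cana's other supports during the study. The background in Section 3 already credits the people Cana supports with better overall and mental health, before CanaCare exists. A time effect cannot separate the two sources.

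What is at stake is the headline conclusion. This is the only primary hypothesis, and Section 13 plans journal papers, conference presentations and presentations to the public. As worded, p < 0.05 for time would read as confirmation that CanaCare works.

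**Working it through.** **1. What the sample size is for.** Inputs from the Section 6.2 table: standardised change 0.38, two-sided alpha 0.05, power 0.80. For a paired (one-sample) t-test the noncentrality is d × √n = 0.38 × √57 = 2.87 on 56 degrees of freedom. Power is 0.805, and 57 is the smallest n that reaches 0.80. The second row also reproduces: d = 0.75 gives n = 16 with power 0.801. The stated figures are therefore correct, and they are figures for a single group's change.

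**2. The observed rise that reaches significance.** The protocol gives a baseline SD of 0.84 but no SD of change. If the SD is the same at both times and r is the correlation between them,

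SD of change = 0.84 × √(2 × (1 − r)),

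which equals 0.84 when r = 0.5. The smallest significant mean change, before covariate adjustment, is

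t(0.975; 56) × SD of change / √57 = 2.003 × 0.84 / 7.550 = 0.22 points.

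Since r is an assumption, the range is:

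| r | SD of change | Smallest significant mean rise (points) |
|---|---|---|
| 0.3 | 0.99 | 0.26 |
| 0.5 | 0.84 | 0.22 |
| 0.7 | 0.65 | 0.17 |
| 0.8 | 0.53 | 0.14 |

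All of these lie below the planning change of 0.33 points. The threshold is the same whether the rise comes from CanaCare or from something else.

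**3. How often a non-programme shift would be declared an improvement.** Suppose that CanaCare adds nothing and scores drift upward for other reasons. With n = 57:

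| True shift (in SDs of change) | Points, if SD of change is 0.84 | Chance of a significant improvement |
|---|---|---|
| 0 | 0 | 2.5% |
| 0.1 | 0.08 | 11% |
| 0.2 | 0.17 | 32% |
| 0.3 | 0.25 | 60% |
| 0.38 | 0.32 | 80% |

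These are conditional figures. Nothing in the documents says which row applies.

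**4. The claim against the design.**

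| Element | What it supports |
|---|---|
| Section 4, primary hypothesis and secondary aims | An effect caused by the programme |
| Section 6.2, sizing | Change within one group |
| Section 6.4, model | Change over time, with no contrast between groups |
| Section 6.3, setting | CanaCare and usual supports together |

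Covariates in Section 6.4 can reduce residual variance or describe who changed. They do not supply the missing comparison.

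**The case against.** The strongest reply is that the statistical sections are already descriptive. Section 6.2 speaks of detecting a change and Section 6.4 of outcomes over time. Section 13 says only that outcomes will be published, so it is a prediction, not a plan, that the result will be presented as an effect of CanaCare. A single-group study is a reasonable choice for a volunteer-run service, and its arithmetic is right. All of this stands. It means that the primary analysis needs no repair, but the hypothesis that the analysis is meant to test remains causal.

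A reader might go further and infer that a significant time effect is to be expected even if CanaCare adds nothing. The documents do not support that:

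- Entry (Section 6.5.1) is open to any adult who expresses interest, with no happiness-score threshold. Regression to the mean is possible but not shown. One could choose an entry deficit and a correlation that make it equal the whole 0.33 points, but that figure would be solved for and not derived.
- People with an acute condition may enrol once treatment is complete, so part of their recovery may precede baseline.
- Cana's supports are called usual, and participants already have contact with Cana. Supports in place before baseline need not produce a change after it, and the protocol does not say when they start.

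A second baseline questionnaire at the participant case conference may also look like a remedy. Under Section 6.3, goal-setting, assessments and possibly counselling come before that conference, so the second score could already reflect the programme. It would also not isolate the concurrent supports.

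Finally, a statistical analysis plan may exist, but it could not create a comparison group, and the hypothesis is fixed in the protocol.

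**Conclusion.** The point holds as a mismatch between the stated hypothesis and the design. Section 4 attributes improvement to CanaCare; Sections 6.1 to 6.4 can establish only that mean scores changed among people receiving CanaCare together with usual Cana supports.

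The size that can be stated is the threshold: an observed mean rise of about 0.22 points reaches p < 0.05 at n = 57, on the assumption that the SD of change is 0.84 (0.14 to 0.26 points for r from 0.8 to 0.3). How much of any rise would come from concurrent supports, natural recovery or regression to the mean cannot be derived from the documents. The finding is not that a false positive is likely, that the sample size is wrong, or that the design is unacceptable. It is that a positive result would not establish the hypothesis as written.

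**What to change.** Four changes of wording:

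1. **Primary hypothesis (Section 4):** mean Oxford Happiness Questionnaire score will improve from baseline to 6 months among participants receiving CanaCare in addition to usual Cana supports.
2. **Secondary aims (Section 4):** describe each as change from baseline, not as an effect of the study.
3. **Section 6.1:** name the design as a single-group before-after study.
4. **Section 6.4:** state that a significant time effect will not be attributed to CanaCare alone.

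No change to the sample size, visits or model is needed. The cost is a more modest headline claim.

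Keeping the causal wording would require a comparison group, which is a different study. As an illustration, detecting a between-group difference of 0.38 SD with 80% power needs about 110 participants per group, or 220 in total, without baseline adjustment. Dividing the planned 57 into two groups would give about 30% power. Rewording is the proportionate course.
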